Participants will wear an activity monitor for one week per month. This will allow us to collect average physical activity across one week time periods which will be used to analyze the impact of the intervention outside of the structured exercise sessions of the endurance exercise group. This will allow us to determine if the endurance exercise group alters its overall activity level over the 6 month time period.

- c) Change from baseline to 6-months for brain imaging measures including the following:
- 1) Hippocampal volumes on structural MRI,
 - 2) Microstructural integrity of white matter pathways on diffusion tensor imaging (DTI),
 - 3) Functional connectivity among brain networks on resting state fMRI,
 - 4) Responses to task-based fMRI Digit Symbol Substitution Test.
- d) Change from baseline to 6-months for biospecimen measures including the following:
- 1) Salivary cortisol measurements; in addition, changes in salivary cortisol measures collected over 8 time points on two consecutive days will be explored at the pre-test and the post-test. We will measure cortisol at time points 0 minutes, 15 minutes, 30 minutes, 45 minutes after the person wakes up.(Stalder, Kirschbaum et al. 2016) In addition, we will measure cortisol at 3 hours, 6 hours, 9 hours and 12 hours after awakening.(Edwards, Clow et al. 2001)
 - 2) Soluble inflammatory biomarkers in plasma
 - 3) Peripheral levels of neurotrophic factors in plasma

PROTOCOL TITLE: Mild Cognitive Impairment and Endurance Exercise in Parkinson's Disease

e) We will collect the NINDS common data elements (CDE) for sex, ethnicity, date-of-birth, education level, family history, and employment status.

- 8.2. Safety Endpoints: There are no safety endpoints, but all participants will be monitored for safety and for adverse events.

Adverse Events (AEs) are defined as exercise-related discomforts (e.g., muscle and joint soreness/pain), minor injuries (e.g., strains, sprains), and non-injurious falls; and attrition is defined as the number of participants who withdraw from the study. Serious Adverse Events (SAEs) are defined as hospitalization, surgery, death, or permanent disability. We will keep detailed logs of all the training sessions so that we can monitor their progress in the endurance exercise program and assess compliance, which we will take to be completion of 80% of the prescribed exercise sessions.

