 - MRI Imaging: All potential participants will be screened for eligibility for a MRI scan as per Radiology guidelines for safety precautions including cardiac pacemaker, metallic implants of any kind in the body, pregnancy, among others. Prior to entering the MRI scan, subjects will be asked again about these safety precautions to determine eligibility for MRI scan. Other possible risks include claustrophobia, boredom, noise, or discomfort from lying supine which will be minimized by talking with the subject periodically during the scanning, providing ear plugs, and providing cushioning. The movement tests are associated with minimal risks, such as stiffness or pain from performing maximal voluntary contractions. This risk will be minimized by providing rest breaks between trials, excluding participants who experience hand pain or other adverse events, and monitoring discomfort. If an individual requires emergency medical care, 911 will be called immediately. This has never happened previously and we have tested more than 100 individuals.
 - Exercise testing: We are using an endurance exercise protocol that we have extensive experience with. Participants are very closely supervised over the first 2 weeks of training to make sure that they are safe and can perform the exercise protocol.
 - Medication withdrawal: All subjects are offered hotel

PROTOCOL TITLE: Mild Cognitive Impairment and Endurance Exercise in Parkinson's Disease

accommodations near the testing facility on the nights prior to testing days during which they are asked to withdrawal from anti-Parkinsonian medication in order to avoid the need to commute to the testing facility while off medication. A research assistant will meet the subjects each morning at the hotel and will accompany the subject via wheelchair, if needed, to the testing facility.

- The risk associated with blood draws are minimal and are reduced in this study because trained personnel who have extensive venipuncture experience, and are trained in aseptic technique, will implement the blood drawing procedures in a clean room.

- No drugs and devices will be used in the research - NA.

- Data collection forms will be used to record the study data and are attached. Forms for test measures are attached for the following tests:
 1. SCOPA-Cog
 2. NINDS Demographics, CDE
 3. MDS UPDRS parts 1,2, 3 (motor) and 4
 4. PD Neurol QOL,

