11.0 Data and Specimen Management

- 11.1* We are collecting pilot data primarily for feasibility, though statistical analyses may be conducted to provide descriptive data of the subject cohort, baseline and 6-month test scores, and potentially exploratory analyses of change in outcome measures or correlations of variables.
- 11.2* Since we are collecting pilot data, there is no power analysis.

PROTOCOL TITLE: Mild Cognitive Impairment and Endurance Exercise in Parkinson's Disease

- 11.3* The research will be conducted in compliance with state and federal laws, including the Health Insurance Portability and Accountability Act (HIPAA) that require researchers to protect and maintain confidentiality of an individual's health information. All subjects will be asked to sign an "Authorization To Use and Disclose (Release) Health Information For a Research Study". Access to all study datasets will be password protected. All research staff will be trained in proper research procedures. We have extensive experience in data capture, data flow and data management based on our SPARX Phase II clinical trial.(Moore, Schenkman et al. 2013) We will use REDCap (Research Electronic Data Capture) to define and manage our own data collection forms. This service is provided through the Northwestern University Clinical and Translational Institute.
- 11.4* Quality control is addressed at the point of data collection, data entry, and data analysis.
- Imaging – the imaging center conducts tests for quality control of the imaging data. A quality control scan is run every day before data acquisition begins.
 - All of our data is double checked for accuracy by a member of our research team. Periodically we have our data checked by a person who is not directly involved in the laboratory.
- 11.5* Study-wide handling of data and specimens is described below:
- Our data consists of analog data and text.
 - Our data is stored on hard disks and backed up regularly.
 - Our data is stored indefinitely.
 - The clinical coordinator, statistician and students and post- doctoral fellows will have access to the data.
 - The clinical coordinator is responsible for receipt of the data.
 - The data will not be transported.
 - The cortisol data will initially stored in a freezer at -80°C before being shipped out for analysis.

12.0 Provisions to Monitor the Data to Ensure the Safety of Subjects:

This study does not involve more than minimal risk.

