14.0 Risks to Subjects*

14.1 Overall, potential foreseeable risks associated with participation in the study are very unlikely and of low risk.

- The potential risks of endurance exercise includes injury to tendons, ligaments, joints, and muscles. There is little likelihood of any physical risk as a result of participation in this research project. The exercise and testing procedures have been well established for people with Parkinson's disease. The use of a well-trained personal trainer further reduces any possible risks.
- During exercise testing there is a chance that subjects could fall, feel pain in their muscles or joints, feel dizzy or faint, have irregular heartbeats, have a stroke or heart attack, or die. The risk of death from an exercise stress test has been estimated to be 1 in 100,000. The risk of a heart attack is about 4 in 10,000 and the risk of a problem that would require hospitalization (for example, chest pain) is about 2 in 1,000. To minimize this risk, only subjects at low to moderate risk will be allowed to participate in exercise testing. Subjects can request to terminate the exercise test at any point during testing. ACSM subject screening and testing guidelines will be followed. The exercise test will be administered by an exercise physiologist who is Advanced Cardiac Life Support (ACLS) certified and has automated external defibrillator (AED) experience. The exercise physiologist administering the test will also have knowledge of appropriate contraindications, risk, and risk assessment of testing, the absolute and relative indications for termination of the exercise test, knowledge of cardiac arrhythmias, and the ability to recognize and treat serious arrhythmias if they arise.
- There are no known hazards to diffusion magnetic resonance imaging, functional magnetic resonance imaging, other than the discomfort associated with confinement and remaining stationary for the duration of the testing procedure. We have found that training in the MR simulation scanner helps to reduce the stress associated with the noise and confinement of the actual MR scanner environment. Testing of all participants will be terminated immediately should they become distressed. We will carefully screen out individuals who have an implanted electrical device (such as a cardiac pacemaker or a neurostimulator), or a certain type of metallic clip (i.e., an aneurysm clip

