PROTOCOL TITLE: Mild Cognitive Impairment and Endurance Exercise in Parkinson's Disease

in the brain). These devices can malfunction and cause harm to the patient in the magnet environment. We will also carefully screen individuals who are claustrophobic to reduce any adverse events. We anticipate that most patients will come by limousine to the testing facility when off medication. Under no circumstance will we allow a patient to drive when off medication.

- Risk associated with blood draws: pain, a bruise at the point where blood is taken, redness and swelling of the vein and infection, and a rare risk of fainting. These risks associated with blood draws are minimal, and are reduced in this study because trained personnel who have extensive venipuncture experience, and are trained in aseptic technique, will implement the blood drawing procedures in a clean room.

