26.0 Compensation for Research-Related Injury

- 26.1 Minimal risk is when the probability and magnitude of harm or discomfort anticipated in the proposed research are not greater, in and of themselves, than those ordinarily encountered in daily life or during the performance of routine physical or psychological examinations or tests. The proposed research does not exceed minimal risk. In the event of research-related injury, subjects will not be compensated for medical care required because of an untoward outcome resulting from participation in the research study. Subjects should seek medical treatment through his or her doctor or treatment center of choice.
- 26.2 If a participant becomes ill or get an injury or illness as a result of study (medications, devices or procedures), they should seek medical treatment through their doctor or treatment center of choice. They should promptly tell the study doctor about any illness or injury. The hospital [university, researchers] will not pay for medical care required because of a bad outcome resulting from their participation in this research study. This does not keep them from seeking to be paid back for care required because of a bad outcome.

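### Section 9.3 describes the movement-test risk through a task this study does not run, leaving off-medication falls unnamed; separately, 12.0 states no study-level safety review or pause rule

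*Combined protocol and SAP*

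**What the plan says.** Within its MRI bullet, section 9.3 turns to the behavioral tests and states: "The movement tests are associated with minimal risks, such as stiffness or pain from performing maximal voluntary contractions". The mitigation that follows is rest breaks, excluding people with hand pain or other adverse events, watching for discomfort, and calling 911 in an emergency.

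Section 9.2 sets the last antiparkinsonian dose at 8:30 pm or earlier on the evening before Day 2. From 10:30 to 11:30 on Day 2 it schedules MDS-UPDRS Part III, the mini-BESTest, three Timed Up and Go trials, the six-minute walk and two questionnaires. Section 9.3 offers a hotel stay and a morning escort, by wheelchair where necessary. Section 14.1 adds: "Under no circumstance will we allow a patient to drive when off medication".

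The full text of 12.0, the section for data monitoring to protect subjects, is "This study does not involve more than minimal risk". Section 26.1 says the same ("The proposed research does not exceed minimal risk"). It defines minimal risk as risks "not greater, in and of themselves, than those ordinarily encountered in daily life" or in routine examinations.

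For exercise testing, 14.1 says the risk of "a problem that would require hospitalization (for example, chest pain) is about 2 in 1,000". Section 8.2 states that "Serious Adverse Events (SAEs) are defined as hospitalization, surgery, death, or permanent disability" and that "all participants will be monitored for safety and for adverse events".

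**The concern.** There are two separate gaps.

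First, the risk text for the movement tests does not match the tests. A rater who relied on 9.3 would look for stiffness and hand pain. The more obvious hazard is a fall during balance, turning and walking tasks in people up to Hoehn and Yahr stage 3 (section 3.2) whose medication has been withheld overnight for research. Anyone judging the risk from 9.3 and 14.1 would not see that hazard named.

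Second, 12.0 puts a classification where a procedure should be. The study includes a maximal exercise test, medication withdrawal, and 6 months of training at 80–85% of maximal heart rate, much of it off site. The plan does not say who looks at adverse events across participants, how often, or what would pause a procedure. What is at stake is participant safety and the completeness of the safety sections. No endpoint or analysis is affected.

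**Working it through.** The plan states no figure to reproduce, and 11.2 says there is no power analysis. The check is mainly a comparison of sections.

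**1. Tests described against tests run.** The endpoints (8.1), visit procedures (9.2), forms list (9.3) and Table 1 contain no maximal contraction or hand-force task. The movement tests listed are MDS-UPDRS Part III, mini-BESTest, Timed Up and Go and six-minute walk. The example in 9.3 therefore matches no listed procedure.

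**2. Time off medication (9.2).**
- Last dose to session start: 20:30 to 10:30 = 14 hours.
- Last dose to session end: 20:30 to 11:30 = 15 hours.

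Both are minimums, because 8:30 pm is the latest permitted dose. No sentence says the tests are done off medication. It is inferred from the dose cut-off, from the withdrawal text in 9.3, 14.1 and 27.1, and from the absence of any morning dose.

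**3. What is said about the off state.**
- 9.3: lodging, escort, wheelchair.
- 14.1: travel and driving.
- Falls: 14.1 names them only under exercise testing. The graded exercise test is on the afternoon of Day 1, before the first withdrawal night.

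Nothing addresses the off state during the balance and walking tests themselves.

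**4. Section 12.0 against 26.1.** The benchmark in 26.1 is daily life or routine examinations. The plan also treats a participant off medication as unfit to drive and possibly in need of a wheelchair. It gives exercise testing a hospitalization risk of about 2 in 1,000, and 8.2 counts hospitalization as serious. These sit uneasily with a bare minimal-risk statement.

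**5. Size.** Inputs: up to 16 participants (23.1), one exercise test each at intake (9.2), rates from 14.1, two withdrawal nights (27.1).
- Expected hospitalizations from the exercise test: 16 × 0.002 = 0.032.
- Chance of at least one: 1 − (1 − 0.002)^16 = 3.15%.
- Chance of at least one heart attack at 4 in 10,000: 1 − (1 − 0.0004)^16 = 0.64%.
- Baseline withdrawal exposure: 16 × 2 = 32 participant-nights. If the 6-month visit repeats the schedule (an assumption; no day plan is given), 16 × 4 = 64.

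The first three figures describe the Day 1 exercise test only. They may be high for this sample, since 14.1 restricts that test to people at low to moderate risk. The documents give no fall rate for the off-medication tests, and none is assumed.

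**6. Oversight that is stated.**
- 8.2 and Table 1: adverse events and SAEs recorded, monthly in Table 1.
- 9.2: weekly review of heart-rate files and adherence by the exercise research assistant.
- 13.1: an investigator may withdraw an individual for injury or illness.
- 20.2: weekly staff meetings, described as being about duties.

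None of these names a reviewer of events across participants or a condition for pausing a procedure.

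**The case against.** The strongest reply is that the plan is not silent on safety. The example in 9.3 is introduced as an example, not a full list. The mitigation reaches other adverse events as well as hand pain. Section 14.1 calls the testing procedures well established in Parkinson's disease and provides for stopping if a participant is distressed. Section 8.2 counts non-injurious falls as adverse events. The exercise test has ECG screening, contraindications, an ACLS-certified physiologist and exclusion of people at high cardiovascular risk. This is a single-site pilot of at most 16 people, and the attached consent form and test forms, not seen here, may hold further precautions.

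All of this stands. It means the assessment is generic rather than absent, and that event capture and individual withdrawal exist. It does not supply a fall precaution matched to the tests, a study-level reviewer or a pause rule in the protocol text.

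Four stronger readings are tempting, and the documents do not support them:
- **That the contraction sentence drives the minimal-risk conclusion.** Neither 12.0 nor 26.1 cites 9.3. Section 14.1 openly lists heart attack and death from exercise testing, and the plan still concludes minimal risk.
- **That the study has no safety monitoring.** This is true of 12.0 alone; 8.2, Table 1 and 13.1 say otherwise.
- **That the refusal of injury compensation rests on the classification.** The two are only adjacent in 26.1, and 26.2 repeats the refusal without mentioning minimal risk.
- **That the 3.15% measures the off-medication hazard.** It belongs to the exercise test, whose risk is disclosed and mitigated.

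**Conclusion.** The point holds as two modest, independent corrections. The movement-test wording in 9.3 fits a different kind of study and leaves falls and worse off-medication symptoms unnamed for tests run at least 14 hours after the last dose. Section 12.0 gives a classification instead of a review procedure, and that classification fits poorly with the definition in 26.1.

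The exposure is small in absolute terms: 32 withdrawal nights, or 64 under the 6-month assumption. The size of the fall risk cannot be derived from the documents. The conclusion rests on the inference that Day 2 testing is off medication, and on the protocol text alone. Whether the study formally meets the minimal-risk definition is for the IRB to decide; this point does not decide it.

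**What to change.** **Sections 9.3 and 14.1.** Replace the contraction and hand-pain text with falls and worse symptoms while off medication. State that the existing rater guards closely during the balance and walking tests and stops a test when needed. In 14.1, list overnight withdrawal and the off-medication tests among the risks.

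**Section 12.0.** Replace the single sentence with a short plan:
- An existing investigator, for example the movement-disorders co-PI, reviews the adverse-event and SAE data already captured monthly.
- SAEs are reported to the IRB.
- Any SAE during testing or training pauses that procedure until it has been reviewed.

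**Section 26.1.** Leave the formal classification to the IRB, with the completed risk list before it.

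**Cost.** A few lines of text, with no new visit, participant assessment or data item. Guarding becomes an explicit duty of a rater already present. Monthly review over 18 months of accrual plus 6 months of follow-up is 18 + 6 = 24 reviews. At an assumed 15 to 30 minutes each, that is 24 × 0.25 = 6 to 24 × 0.5 = 12 hours of existing investigator time across the study. A pause after an SAE could delay some testing or training sessions.

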 5. MOCA
 6. Pittsburgh Sleep Quality Index,
 7. Epworth Sleepiness Scale,
 8. Fatigue Severity Scale,
 9. Hamilton Depression Scale,
 10. Health-related quality of life (PDQ-39),
 11. Mini Balance Evaluation Systems Test
 12. Timed up and Go (3 trials)
 13. Six-minute walk test
 14. Activities-Specific Balance Confidence Scale
 15. New Freezing of Gait Questionnaire
 16. MoCA Alternate version
 17. Symbol Digit Modality Test,
 18. Trail Making Test-Parts A and B,
 19. Raven's Progressive Matrices,
 20. Clock Drawing,
 21. Hopkins HVLN-R,
 22. Free and Cued Selective Reminding Test,
 23. Figural memory test, ,
 24. Boston Naming Test,
 25. Verbal fluency [semantic - animals, phonemic - letters],
 26. Judgment of Line Orientation,
 27. Intersecting pentagons,

9.4 The data that will be collected is outlined in Table 1.

PROTOCOL TITLE: Mild Cognitive Impairment and Endurance Exercise in Parkinson’s Disease

Table 1 Dependent Measures	Baseline	Each ex session	Each mo	6 mo
Primary Measures				
Cognitive Measures: Symbol Digit Modality Test, Trail Making Test-Parts A and B, Raven’s Progressive Matrices, Clock Drawing, Word list learning and delayed recall, Free and Cued Selective Reminding Test, Figural memory test,	X			X
Secondary Measures				
National Institute of Neurological Disorders and Stroke common data elements	X			
MDS-UPDRS I, II, IV	X			X
Sleep (Pittsburgh Sleep Quality Index, Epworth Sleepiness Scale)	X			X
Fatigue (Fatigue Severity Scale)	X			X
Mood (Hamilton Depression Scale)	X			X
PDQ-39	X			X
Cognitive Measures: Boston Naming Test, Verbal Fluency, Judgment of Line Orientation, Intersection pentagons, Spatial working memory	X			X
MDS-UPDRS III	X			X
Neuro-QOL	X			X
Mini Balance Evaluation Systems Test (Mini-BESTest)	X			X
Timed Up and Go	X			X
6 minute walk test	X			X
Activities-Specific Balance Confidence Scale (ABC scale)	X			X
New Freezing of Gait Questionnaire (NFOG-Q)	X			X
Activity Monitor			X	
MRI: Hippocampal volumes	X			X
MRI: DTI measures	X			X
MRI: Functional connectivity	X			X
Serious Adverse Events (SAEs) and Adverse Events (AEs)			X	
Attrition			X	
EE training log		X		
Levodopa Equivalent	X			X
Cortisol (2 consecutive time points)	X (8)			X (8)
Blood Draw	X			X

PROTOCOL TITLE: Mild Cognitive Impairment and Endurance Exercise in Parkinson's Disease

10.0 Data and Specimen Banking:

- 10.1* The primary investigator and co-investigators will have access to the raw data. Research staff at Northwestern University will be restricted access to the online database for data entry and report generation. Any data viewed by others/collaborators will be de-identified. Hard copies of data collection forms will be stored in a locked office or laboratory. Data entered into spreadsheets will be kept on password protected computer drives.
- 10.2* Participants will be requested to conduct the saliva sampling protocol in their domestic setting on two weekdays. Saliva sampling will commence in the post-awakening period and across the day. Saliva will be collected by salivettes. Prior to saliva sampling (30 min) participants will be instructed to take nil by mouth bar (except water). During the post-awakening period they will be asked to refrain from brushing their teeth to avoid abrasion and vascular leakage. SMS text messages will be used to send reminders to participants to complete saliva samples. Electronic devices will be used to record awakening and saliva sampling times (actigraph & trackcaps respectively). Participants will receive detailed verbal and written instructions on the study protocol. Saliva samples will be stored in the freezer at -80°C in a special purpose laboratory on the 7th floor of [name]. For salivary cortisol assay, the Salimetrics High Sensitivity Salivary Cortisol Enzyme Immunoassay Kit will be used. This assay captures the full range of salivary cortisol levels (0.003 to 3.0µg/dL) requiring only 25 uL of saliva per test. A built-in pH indicator detects acidic or basic samples.
- 10.3* The data will be shared with Rush University Medical Center. The data will not be identifiable when shared. Cortisol data will be shared with [name] and [name] at the University of Westminster. Data shared with the University of Westminster will be de-identified. Data that can be used for descriptive statistics including but not limited to gender, age, disease duration, MDS-UPDRS scores, and cognitive data will also be shared with the University of Westminster. No data shared with the University of Westminster will be identifiable data.

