1993, Kohrt, Spina et al. 1998) The regimen will include 5-10 min of warm up, 30 min of exercise at target HR and 5-10 min of cool down. They will exercise 3 days per week. The intervention group will be given a HR range to achieve during exercise sessions: 80.0%-85.0% HRmax. During the first 8 weeks of training, exercise duration and intensity will be gradually increased to the target levels. Subjects will be instructed on monitoring HR and adjusting the exercise to remain in the target HR range (i.e., by changing treadmill speed and/or incline). During exercise, subjects will wear a heart rate monitor that captures and stores HR throughout the exercise bout. The exercise Research Assistant (RA) will electronically transfer the HR file from each exercise session (supervised and unsupervised) into the study database.

During the first 2 weeks, subjects must exercise at a main study site under supervision of an Exercise training RA. All 'on-site' exercise sessions will be supervised by an exercise RA. After 2 weeks, the RA will determine whether the subjects may exercise off-site at a community fitness facility or at home to maximize the likelihood of compliance. If the subjects are exercising in their target HR range for the prescribed duration and have demonstrated to the exercise RA that they are able to operate the HR monitor, the subjects will exercise 2X/wk at the main site for 2 weeks and then 1X/wk for 2 weeks. Thereafter, if cleared by the RA, subjects will be expected to exercise on-site at least 1 x/month at the main site. Other exercise sessions will take place at the approved off-site facility. HR monitors must be worn for all sessions. HR data will be downloaded once weekly by an approved person at the facility or brought to a main site to be downloaded by the RA. In addition, the subject will be given an exercise diary log to document his/her wear time sessions on a weekly basis. The RA will check adherence to their prescription each week and will work with the participant as needed to assure appropriate adherence to the protocol.

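### Adverse events are scheduled for collection only once a month, with no stated collection period, so the pilot is likely to under-count minor events

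*Combined protocol and SAP*

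**What the plan says.** Section 9.4 states that "The data that will be collected is outlined in Table 1". The table has four timing columns: baseline, each exercise session, each month and 6 months. The row "Serious Adverse Events (SAEs) and Adverse Events (AEs" carries one mark, under each month.

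Section 8.2 says "There are no safety endpoints, but all participants will be monitored for safety and for adverse events". It then gives the definition: "Adverse Events (AEs) are defined as exercise-related discomforts (e.g., muscle and joint soreness/pain), minor injuries (e.g., strains, sprains), and non-injurious falls". Serious events are defined by outcome (hospitalization, surgery, death, permanent disability). Section 8.2 gives no method, start, end or look-back period.

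For the training period, 9.2 says "The RA will check adherence to their prescription each week", and also provides a weekly diary and heart-rate downloads. Section 8.2 adds a log of every training session. The stated purposes are adherence, wear time, progress and compliance. Section 26.2 asks participants to report any illness or injury promptly to the study doctor. Section 12.0, on monitoring data for safety, says only that the study carries no more than minimal risk.

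**The concern.** Two parts of the study sit awkwardly with a monthly-only mark.

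The first is the test days. The maximal treadmill test is done on baseline Day 1, after consent. The following days bring MRI, a blood draw, and walking and balance tests. Section 9.3 offers a hotel for the nights when participants are "asked to withdrawal from anti-Parkinsonian medication in order to avoid the need to commute to the testing facility while off medication". A fall during these tests would meet the 8.2 definition, yet the schedule shows no collection on those days.

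The second, and weightier, is training. Soreness, strains and falls without injury are easily forgotten. Participants must have mild cognitive impairment (SCOPA-Cog 17 to 24, section 3.2), and most later sessions may be unsupervised. A monthly question is a weak way to capture such events when staff are in touch every week.

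The stake is the tolerability record. Section 11.1 says the data are collected mainly for feasibility, and 2.2 says they will support a later grant application. A record that misses minor events makes the regimen look better tolerated than it was.

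**Working it through.** There is no figure in the plan to reproduce. The check sets the table against the text and then counts sessions.

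**Table 1 marks**

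| Row | Baseline | Each session | Each month | 6 months |
|---|---|---|---|---|
| Adverse and serious adverse events | – | – | X | – |
| Attrition | – | – | X | – |
| Activity monitor | – | – | X | – |
| Training log | – | X | – | – |
| Blood draw | X | – | – | X |

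The monthly column has its ordinary meaning: 8.1 has the activity monitor worn one week per month. The per-session column is in use, for the training log.

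**Collection period.** Sections 8.2, 9.2, 9.3, 12.0, 13, 14.1 and 26.2 give no start, end, look-back period or standard question. None of the 27 forms listed in 9.3 is an adverse-event form, but that list is of test measures, so its silence is weak evidence.

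**Early leavers.** In 9.2, consent is item 1 and the treadmill test item 12 on baseline Day 1. A positive test makes the participant ineligible. Such a person has consented and been exposed to the test, but leaves before any monthly collection falls due.

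**Sessions per collection.** Inputs: 3 sessions a week (9.2) and 6 months (7.1), taken here as 26 weeks.

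- Total: 3 × 26 = 78 sessions.
- Per monthly collection: 78 / 6 = 13.
- Per weekly staff check: 3. There are about 26 such checks, against about 6 monthly collections.

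**Supervision, for someone cleared to train off-site who attends the stated minimum (9.2)**

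- Weeks 1–2: 2 × 3 = 6 on-site. Weeks 3–4: 2 × 2 = 4. Weeks 5–6: 2 × 1 = 2. Sum: 12 of 18.
- Weeks 7–26: 20 × 3 = 60 sessions. At one on-site session a month, 20 / 4.33 = 4.6, so 4 to 5 on-site and 55 to 56 off-site (92% to 93%).
- Overall: 16 to 17 of 78 on-site (21% to 22%).

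Duration and intensity build up over the first 8 weeks, while the on-site minimum falls to monthly after week 6. Direct observation is therefore thinnest once the full regimen is reached.

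**Weight of one participant.** At the maximum of 16, 1 / 16 = 6.25 percentage points of any participant-level event rate.

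**Size of the under-count.** This would need an event rate and the share of events lost between monthly collections. The documents give neither, so no estimate is offered.

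**The case against.** A reader might infer that test-day events fall outside any collection window, or that a site following Table 1 would record none of them. The documents do not support that. They define no window, so a monthly collection could look back to consent or coincide with the 6-month visit. Section 8.2 promises monitoring with no exception for test days, and 9.4 calls the table an outline. Attrition is also marked only monthly, and nobody would conclude that withdrawals at baseline go uncounted. Test days are staffed: an exercise physiologist with advanced life-support certification runs the treadmill test, and testing stops on distress. All of this stands. What remains is that coverage of those days is unspecified, and that a look-back cannot reach someone who left at baseline unless staff record the event separately.

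A reader might also turn to 14.1, which says "The risk of a heart attack is about 4 in 10,000 and the risk of a problem that would require hospitalization" is about 2 in 1,000. Over 16 baseline tests, 1 − (1 − 0.002)^16 = 3.2%. That is the chance that such an event occurs, not that it is missed, and these are the events least likely to go unnoticed. The test is described only for intake, so the figure has no bearing on the 6-month visit.

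Finally, monthly recall is not the only route, and it would be wrong to call participants memory-impaired: mild cognitive impairment under 3.2 does not require a memory deficit. For those cleared off-site, 10 of the first 12 sessions are supervised, staff make weekly contact, a carepartner lives in the home, and 26.2 asks for prompt reporting. But the logs, diary and weekly check are not described as capturing adverse events, the carepartner has no stated reporting role, and 26.2 covers illness or injury, which a fall without injury is not.

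**Conclusion.** The concern holds in a limited form. The only stated schedule collects adverse events monthly, about 13 sessions apart, and no section gives the collection period. For test days the gap is one of specification: serious events would probably be seen, but the plan does not say they are recorded. For training, the schedule is likely to under-count soreness, strains and non-injurious falls in the tolerability data of a feasibility pilot.

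The direction of the bias is a judgement, resting on minor events being easily forgotten, participants being cognitively impaired, and most sessions after week 6 being off-site. The session counts assume 26 weeks, clearance for off-site exercise and attendance at the stated minimum; participants kept on-site would be better observed. The documents do not show that serious events would be lost, nor how large the under-count would be.

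**What to change.** - In 8.2, state that adverse and serious adverse event collection runs from consent to the last post-test day, including participants found ineligible at the baseline exercise test.
- In Table 1, keep the monthly mark and add marks at baseline, at each exercise session (through the existing training log) and at 6 months.
- In 9.2, add a fixed adverse-event, fall and symptom item to the weekly diary and to the research assistant's weekly check, with carepartner input where available.

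This uses contacts and records that already exist and changes no treatment or clinical rule. The cost is protocol wording, a line on the log and diary, and a few minutes a week. The downside is more minor events to log and a less favourable reported rate.
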